**Supplemental Table 1. Events in all Patients**

Data expressed as nr of patients with event (% of patients) and total nr of event reported.

\*defined as Systolic arterial pressure < 80 mmHg over 30 minutes

Supplemental Table 1. Events in all Patients

### **iii. Analysis of adverse events**

Intention- To -Treat (ITT): adverse events will be reported as rates: total nr of events per patient and compared intervention arm vs standard of care arm using Chi square test with two-sided p-values.

Safety population are the patients who received at least once the study drugs (hydralazine and/or nitrates in the form of capsules, spray and/or transdermal application), and events are reported up to last confirmed intake of the study drug.

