### **8.2 Statistical Analysis**

The statistical analyses will be performed using the SPSS / PC (version 14.0, SPSS Inc., USA) software package. A statistical significance level (p-value) of 0.05 will be used. All data will be analyzed on an intention-to-treat basis. Comparisons will be made using the t-test, Mann Whitney U-test, Fisher's exact test, survival analysis (Kaplan Meier method), Cox regression analysis and chi-square test as appropriate. All hypothesis testing will be two-tailed. Statistical support will be performed by [name] from the Institute of Social and Preventive Medicine of the University of Basel.

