### b. Secondary objectives

Secondary endpoints are:

- All-cause mortality at 180 days.
- HF re-hospitalization at 180 days.
- Death or re-hospitalization from all causes at 180 days.
- Need for ICU admission during initial hospitalization.
- Acute coronary syndrome during initial hospitalization.
- Symptomatic hypotension during initial hospitalization.
- B-type natriuretic peptide (BNP) and creatinine level at 48 h and at discharge.
- Changes in circumferences of both legs and central venous pressure during hospitalization.
- Change in patient-assessed dyspnea at 48 h and prior to discharge.
- Blood pressure course over the first 6 days.
- Time to disappearance of a third heart sound (if present initially).
- Time to discharge.
- In-hospital days for HF at 180 days and 360 days.
- Total treatment cost at 180 days and 360 days.
- Functional status at 180 days and 360 days.
- Quality of life (EQ-5D-3L) at 180 days and 360 days.
- Fractures due to falls within 180 days and 360 days.
- Death or HF re-hospitalization at 360 days.

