**ee. Method for analysis**

**i. Binary data**

Binary data will be compared Intervention arm vs Standard of care using Fisher's exact test for 2 x 2 tables with two-sided p-values.

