**ii. Count data**

Count data will be compared Intervention arm vs Standard of care using Pearson's chi-squared test with two-sided p-values.

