#### ii. Display of adverse events

A supplementary material table will be produced with all adverse events if applicable and requested:

	Nr of patients with the event	Total nr of events	% of events intervention stopped	Nr of patients with the event	Total nr of events	% of events intervention stopped	p-value
Adverse events							
Headaches	xx(%)	xx	xx%	xx(%)	xx	xx%	x.xx
Dizziness	xx(%)	xx	xx%	xx(%)	xx	xx%	x.xx
Fall	xx(%)	xx	xx%	xx(%)	xx	xx%	x.xx
Creatinine increase > 30% of baseline	xx(%)	xx	xx%	xx(%)	xx	xx%	x.xx
Hypokalemia < 3.5 mmol/l	xx(%)	xx	xx%	xx(%)	xx	xx%	x.xx
Hyperkalemia > 5 mmol/l	xx(%)	xx	xx%	xx(%)	xx	xx%	x.xx
Arrhythmia requiring therapy	xx(%)	xx	xx%	xx(%)	xx	xx%	x.xx
Systolic arterial hypotension*	xx(%)	xx	xx%	xx(%)	xx	xx%	x.xx
Acute coronary syndrome	xx(%)	xx	xx%	xx(%)	xx	xx%	x.xx
Transfer to the intensive care unit	xx(%)	xx	xx%	xx(%)	xx	xx%	x.xx
Cardiopulmonary resuscitation	xx(%)	xx	xx%	xx(%)	xx	xx%	x.xx
Serious adverse events							
Death	xx(%)	xx	xx%	xx(%)	xx	xx%	x.xx
In-patient hospitalization	xx(%)	xx	xx%	xx(%)	xx	xx%	x.xx
Prolongation of existing hospitalization	xx(%)	xx	xx%	xx(%)	xx	xx%	x.xx
SAE other than any of the above	xx(%)	xx	xx%	xx(%)	xx	xx%	x.xx

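### The adverse event comparison, read literally, applies a chi-square test to event totals, which can overstate significance when patients have repeat events

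*Combined protocol and SAP*

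**What the plan says.** SAP 11.1.3 (Analysis of adverse events) says that adverse events are reported as rates, "total nr of events per patient and compared intervention arm vs standard of care arm using Chi square test", with two-sided p-values. It gives no table layout, no unit of analysis and no allowance for several events in one patient.

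SAP 11.1.2 (Display of adverse events) sets out Supplemental Table 1. For each arm it has one column for patients with the event and another for the total number of events, but there is a single p-value column. The table note reads "Data expressed as nr of patients with event (% of patients) and total nr of event reported" and does not link the p-value to either quantity. The table itself is conditional: "A supplementary material table will be produced with all adverse events if applicable and requested".

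For patient-level yes/no data, SAP 10.2.1 names a different test: "Binary data will be compared Intervention arm vs Standard of care using Fisher's exact test". Protocol 8.2 sets the level: "A statistical significance level (p-value) of 0.05 will be used". SAP 6.6.4 says that p-values from secondary analyses are not read against a threshold, but it does not mention safety analyses.

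**The concern.** A chi-square test on event totals has the correct variance only if events behave like independent (Poisson) counts. Here repeats in the same patient are likely. Several of the events in SAP 11.1.1 are threshold crossings of quantities measured again and again: potassium, creatinine and systolic pressure. Protocol Section 5 has creatinine and electrolytes measured every 24 to 72 hours in the first week. After symptomatic hypotension on day 1 or 2, blood pressure is checked every 30 to 60 minutes, so a first episode raises the chance of recording another. Neither document says when a repeat abnormal value counts as a new event. Re-hospitalization, collected as a serious adverse event to 180 days, can also recur.

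Safety is part of the primary objective in SAP 2.1, and Protocol Section 6 names hypotension with reduced organ blood flow as the main risk of the intervention. A small p-value produced by a few patients with many events could be taken for a difference between the arms.

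**Working it through.** The plan states no error rate or power for this test, so there is no figure of its own to reproduce.

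**Inputs**
- From the documents: 385 patients per arm (SAP 3.2), 1:1 allocation (SAP 3.3), two-sided 0.05 (Protocol 8.2).
- Assumed: V, the variance-to-mean ratio of the number of events per patient, from 1 to 3. For the simulation, also a mean of 0.5 or 1.0 events per patient.
- Assumed layout: the two event totals are compared against an equal split, because the SAP gives no layout.

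**Step 1: formula.** Let A and B be the event totals, n the patients per arm and m the mean events per patient, equal in both arms. The statistic is (A − B)² / (A + B), compared with 3.84.
- The true variance of A − B is 2nVm.
- The denominator A + B is about 2nm.
- The signed root therefore has variance V instead of 1, and the true type I error is 2 × [1 − Φ(1.96/√V)]. It does not depend on n or m.

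**Step 2: numbers.** The simulation used 10,000 null trials per scenario, with 385 patients per arm and Poisson or negative binomial counts (V = 1 + km, where k is the dispersion).

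| V (assumed) | 1.96/√V | Formula | Simulated, mean 0.5 | Simulated, mean 1.0 |
|---|---|---|---|---|
| 1 | 1.960 | 0.050 | 0.048 | 0.052 |
| 1.5 | 1.600 | 0.110 | 0.107 | 0.110 |
| 2 | 1.386 | 0.166 | 0.164 | 0.166 |
| 3 | 1.132 | 0.258 | 0.262 | 0.254 |

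Formula and simulation agree.

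**Step 3: events that occur at most once.** If a fraction p of patients have the event once, V = 1 − p, which is below 1. The same test then becomes conservative: 0.044 at p = 5% and 0.019 at p = 30% by simulation.

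**Step 4: patient as the unit.** Over simulated means of 0.1 to 1.0 and k from 0 to 4, comparing patients with at least one event (2 × 2 chi-square) gave 0.046 to 0.054. Comparing mean counts with a variance estimated from the patients gave 0.047 to 0.055. Both hold the nominal level. Fisher's exact test and the negative binomial and robust Poisson models were not themselves simulated; they also take the patient as the unit.

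**The case against.** The strongest reply is that the quantity tested is not fixed. Supplemental Table 1 shows patients with the event beside total events, and a chi-square on patients would be valid. This stands in part: one cannot say that the table's p-values will be wrong. But the one sentence that states the rule names total events. The table keeps the two quantities apart, and the SAP assigns patient-level binary data to Fisher's test rather than chi-square. A test on totals is therefore the natural reading, and on the kinder reading the choice remains open until the data are seen.

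A second reply is that the inflation is conditional and its size unknown. This stands. With Poisson counts there is none, and collecting the listed non-serious events only during the index stay (SAP 11.1) limits repeats.

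A third is that little depends on it. This also largely stands. The table is supplementary and conditional. SAP Table 3 separately reports symptomatic hypotension, acute coronary syndrome and ICU admission as numbers and percentages with a hazard ratio.

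A reader might go further and infer that the general rule, "Count data will be compared Intervention arm vs Standard of care using Pearson's chi-squared test", carries the same fault into endpoints such as "In-hospital days for HF at 180 days and 360 days". The documents do not support that. SAP 10.2.2 names neither that endpoint nor totals. SAP 10.1.2 sends secondary endpoints to the approach used for the primary endpoint, and SAP 10.2.3 gives the Mann–Whitney test for continuous data. A Pearson chi-square on patients classified by number of events (0, 1, 2, 3 or more) kept 0.034 to 0.055 in the same simulation.

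**Conclusion.** The point holds for SAP 11.1.3 as written. A chi-square on event totals ignores clustering within patients and can inflate false positives for recurrent events. The size rests on an assumed V: about 5% at V = 1, rising to about 26% at V = 3. The documents give nothing from which to estimate V, and once-only events are not inflated. Supplemental Table 1 does not settle whether patients or events are tested.

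The primary endpoint is untouched and the consequence is modest. The correction is still worth making, because these p-values describe the safety of an intervention whose stated main risk is hypotension, and SAP 6.6.4 does not clearly place them under its exploratory rule.

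**What to change.** Amend SAP 11.1.3 in two sentences.
- The p-value for each row of Supplemental Table 1 compares the number of patients with at least one event between the arms by Fisher's exact test, as in SAP 10.2.1; total events are shown descriptively.
- If event rates are tested, use negative binomial regression, or Poisson regression with robust standard errors, with the patient as the unit and log days at risk as offset.

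The offset matters because the listed non-serious events are collected only during the index stay, and the Protocol's Introduction expects a shorter time to discharge in the intervention arm, so the arms may differ in time at risk.

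Repeat the first sentence in the note to Supplemental Table 1. The cost is a short text change made before the data are analyzed. No extra patients are needed, and R, already named in SAP 6.1, fits these models.

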## Summary

**Background:** In contrast to treatment for chronic heart failure, which is based on several large prospective randomized controlled trials, treatment for acute heart failure is largely based on uncontrolled studies, clinical experience and expert opinion. Perhaps at least in part related to the uncertainties in the treatment of acute heart failure, outcome of patients with acute heart failure is extremely poor. Mortality is 50% at three years. More than 85% of patients with acute heart failure are treated in the non-ICU / CCU setting - the Emergency Department and the regular medical ward. Unfortunately, appropriate treatment is particularly ill-defined in this setting.

**Aim:** to test the hypothesis that a comprehensive approach using an early goal-directed decrement of preload and afterload with a target systolic blood pressure of 90 to 110 mm Hg by aggressive vasodilatation in patients with acute heart failure in the non-ICU setting is safe, and leads to a better clinical and economical outcome.

**Methodology:** This is a prospective, randomized, controlled multicenter study designed to enroll 770 patients presenting with acute heart failure at the emergency departments at the participating study sites. Patients will be randomly assigned 1:1 after stratification for site and B-type natriuretic peptide (BNP, NT-proBNP) levels to an early goal-directed therapy or standard care according to current guidelines. Early goal-directed therapy applies aggressive vasodilatation using sublingual and transdermal nitrates, hydralazine to avoid tolerance to nitrates, and rapid up-titration of angiotensin converting enzyme inhibitors and angiotensin II receptor blockers with a target systolic blood pressure of 90mm Hg to 110 mm Hg. Timing and dosing of diuretics and all other treatments are left to the discretion of the treating physician in both groups. The primary endpoint is death or heart failure readmission within 180 days. Secondary endpoints include the quantitative assessment of dyspnea, need for admission to the intensive care unit, surrogate markers like BNP or NT-proBNP, the digitally recorded third heart sound, renal function, time to discharge, functional status and quality of life, falls, total treatment cost, and cost-effectiveness. Patients will receive extensive clinical and economic follow-up of at least 360 days. Endpoints will be adjudicated by a clinical endpoint committee blinded to group assignment.

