## 2. Study objectives

### a. Primary objective

The aim of our study is to determine the safety and efficacy of an early goal-directed preload and afterload decrement with a target systolic blood pressure of 90 mmHg to 110 mmHg by aggressive vasodilatation versus standard medical care in a non-ICU setting in patients with acute HF. The primary endpoint is **death or heart failure re-hospitalization** up-to 180 days of follow-up.

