#### **ii. Other safety evaluations**

##### **11.1.1. Other observations related to safety**

No other safety observations, assessments or analyses are currently defined and planned for this statistical analysis plan.

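### The plan hypothesises safety but sets no criterion for it, and adverse events get p-values without effect estimates or confidence intervals

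*Combined protocol and SAP*

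**What the plan says.** **The aim.** The protocol Summary states the hypothesis that the strategy "in patients with acute heart failure in the non-ICU setting is safe, and leads to a better clinical and economical outcome". The SAP's primary objective (2.1) begins: "The aim of our study is to determine the safety and efficacy of an early goal-directed preload and afterload decrement". The only primary endpoint is the composite of death or heart failure re-hospitalisation at 180 days.

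**The tests.** Protocol 8.2 says "A statistical significance level (p-value) of 0.05 will be used" and "All hypothesis testing will be two-tailed". SAP 11.1.3 has adverse events "compared intervention arm vs standard of care arm using Chi square test with two-sided p-values". SAP 10.2.1 gives binary data in general Fisher's "exact test for 2 x 2 tables with two-sided p-values".

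**The display.** Supplemental Table 1 (SAP 11.1.2) has counts, percentages and a p-value column, with no effect estimate or interval. Of its status the SAP says: "A supplementary material table will be produced with all adverse events if applicable and requested". The closing section on other safety observations adds: "No other safety observations, assessments or analyses are currently defined and planned".

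**What points the other way.** Table 3 (SAP 10.1.4) has a column for the hazard ratio with 95% interval. Its rows include all-cause mortality, ICU admission, acute coronary syndrome and symptomatic hypotension. SAP 6.6.4 treats secondary analyses as exploratory and reads their p-values without a significance threshold.

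**The concern.** A two-sided test of difference takes equal rates as its null hypothesis. It can give evidence of harm, but failure to reject is not evidence that harm is absent. Where the stated hypothesis is safety and a harm has only a p-value beside it, a reader may treat a large p-value as support for that hypothesis.

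This bears on events that matter here. Protocol section 6 names arterial hypotension, with reduced blood flow to the kidneys and other major organs, as the main potential adverse event. The rows for systolic pressure below 80 mm Hg, creatinine rise above 30%, hyperkalaemia, arrhythmia and resuscitation appear only in Supplemental Table 1. Table 3 has related rows (symptomatic hypotension, creatinine level) but not these events. For them the plan gives a p-value and no measure of how large an excess remains compatible with the data.

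**Working it through.** **Inputs from the documents.** 385 patients per arm (protocol 8.3, SAP 3.2), 1:1 allocation, two-sided 0.05.

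**The plan's own figure.** The 385 concerns the composite endpoint only, and it cannot be derived from the documents because no control rate is given. It fits an assumed 50% versus 40%: (1.96 + 0.8416)² × (0.5×0.5 + 0.4×0.6) / 0.10² = 7.849 × 0.49 / 0.01 ≈ 385. No calculation addresses harms.

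**Assumed.** The documents give no adverse event rates, so control rates of 1% to 10% are used. The test is applied to patients with at least one event.

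**Step 1: chance of missing a doubling.** With p̄ the mean of the two rates,

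power = Φ{[(p₂ − p₁) − 1.96·√(2p̄(1−p̄)/n)] / √([p₁(1−p₁) + p₂(1−p₂)]/n)}.

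For 2% versus 4%: the null standard error is √(2×0.03×0.97/385) = 0.01230 and the alternative one is √((0.0196 + 0.0384)/385) = 0.01227. Power = Φ((0.02 − 0.0241)/0.01227) = Φ(−0.33) ≈ 0.37, so the miss rate is 63%. The exact columns enumerate all pairs of counts.

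| Rates | Miss, approximation | Miss, exact chi-square | Miss, exact Fisher |
|---|---|---|---|
| 1% vs 2% | 79% | 82% | 87% |
| 2% vs 4% | 63% | 63% | 70% |
| 3% vs 6% | 48% | 48% | 54% |
| 5% vs 10% | 25% | 24% | 28% |
| 10% vs 20% | 3% | 2% | 3% |

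Using 390 per arm (the SAP's planned enrolment of about 780) changes these by less than one point.

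**Step 2: what an interval would show.** If the true rates are equal, the 95% half-width for the risk difference is 1.96·√(2p(1−p)/385). The matching upper limit for the risk ratio is exp{1.96·√(2(1−p)/(385p))}.

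| Common rate | Half-width, points | Upper limit, risk ratio |
|---|---|---|
| 1% | 1.4 | 4.08 |
| 2% | 2.0 | 2.69 |
| 3% | 2.4 | 2.23 |
| 5% | 3.1 | 1.85 |
| 10% | 4.2 | 1.53 |

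By the risk-ratio limit, even a perfectly neutral result would leave a doubling open at rates of 3% or below.

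**Step 3: an illustration.** Take 8 of 385 (2.1%) in control and 15 of 385 (3.9%) in the intervention arm. The difference is 7/385 = 1.8 points. The pooled rate is 23/770 = 2.99%, with standard error √(2×0.0299×0.9701/385) = 0.0123, so z = 1.48 and p ≈ 0.14. The 95% interval is 1.8 ± 1.96 × 1.23, that is −0.6 to +4.2 points. The p-value alone hides that an excess of up to about four per hundred patients is not excluded.

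**The case against.** The strongest reply is that the plan already estimates the gravest harms. Table 3 gives 95% intervals for mortality, ICU admission, acute coronary syndrome and symptomatic hypotension, and it also has estimate cells for creatinine level and fractures. SAP 6.6.4 declines a significance threshold for secondary analyses. No sentence equates a p-value above 0.05 with safety. This all stands. A reader might infer that harms are examined only by tests of difference, or that the plan would declare safety from non-significance. The documents support neither reading.

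The reply does not close the gap. SAP 6.6.4 does not say whether it covers the adverse event tests, and protocol 8.2 sets 0.05 for the trial generally. The Table 3 intervals are not connected to the safety aim, and the adverse events listed above have no interval.

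A second reply is that the tests are not weak for common events. This also stands. The protocol describes headache as common with nitrates and some creatinine rise as common in acute heart failure. If such events run at 10% or more in the control arm, a doubling is rarely missed.

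A third is that a superiority trial need not fix an acceptable limit for harm. That is fair. With equal true rates, the chance that the 95% limit excludes an absolute excess equal to the control rate is Φ(p/√(2p(1−p)/385) − 1.96): 29%, 51%, 68% and 89% at 1%, 2%, 3% and 5%. A limit would often fail for rare harms even with no true excess. It is a trade-off for the sponsor and is not asked for here.

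**Conclusion.** The concern holds as a gap in reporting and wording. The plan hypothesises safety, gives no criterion for concluding it, and summarises adverse events by p-values without estimates in a table that is not guaranteed to appear. A non-significant p-value could then be taken for safety.

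How much this matters depends on event rates that the documents do not give. The chi-square test is more likely than not to miss a doubling at assumed control rates of 1% and 2%. At 3% it is close to even, at 5% the miss is about a quarter, and at 10% it is negligible. A reader should not infer that a missed doubling is the likely outcome for harms in general.

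**What to change.** - In SAP 11.1.3 and Supplemental Table 1, give for each event the risk difference in patients with at least one event, with its two-sided 95% interval, in place of or beside the p-value.
- Remove the condition on producing the table, so that it is always reported.
- State that non-significance is not evidence of safety, and that safety is described by the upper confidence bounds, including those already planned in Table 3.
- Word the safety aim as estimation.

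The cost is some SAP text and one table column; no further patients or data are needed. The downside is a less favourable safety statement for rare harms, because intervals at this sample size will often not exclude a relevant increase.

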## Study Therapy Early Goal-Directed Group

Early goal-directed preload and afterload decrement with a target systolic blood pressure of 90 mm Hg to 110 mm Hg for the entire hospitalization. This blood pressure target is considered to represent the maximal feasible afterload decrement without impairment of critical organ perfusion (40). This pathophysiologic goal is pursued by predominately applying nitrates, ACE-inhibitors and ARBs at maximal tolerable (avoiding arterial hypovolemia and inadequate arterial perfusion pressure) doses.

The treatment schedule is displayed in Figure 5a. Accordingly, on day 1 (0 h till 24 h) treatment will be started with one capsule of sublingual nitrates (containing usually 0.8 mg glyceryl trinitrate) or two applications of nitrospray (containing usually 0.4 mg

glyceryl trinitrate per application) in combination with transdermal nitrates (for example Nitroderm TTS® 10 mg / 24h) in a dosage between 40 to 80 mg / 24 h depending on admission systolic blood pressure. 10 and 20 minutes after the initial sublingual nitrates capsule or nitrospray application, one additional capsule of sublingual nitrates (containing usually 0.8 mg glyceryl trinitrate) or two applications of nitrospray (containing usually 0.4 mg glyceryl trinitrate per application) will be administered (in total three capsules sublingual nitrates or six applications of nitrospray). After 6 hours a dose adjustment of the transdermal nitrates dependent on systolic blood pressure will be performed (Figure 5a). On day 1 and 2, transdermal nitrates will be applied as continuous therapy for 24 hours each patch. In patients without severe renal dysfunction (defined as calculated glomerular filtration rate below 30 ml/min) and without evidence of an acute coronary syndrome (accompanying chest pain, new ECG changes, elevated cardiac Troponin T), hydralazine will be added orally to achieve an early maximal vasodilative effect and to avoid tolerance to nitrates. Hydralazine will be administered in a fix dosage of 25 mg every 6 hours (1 - 1 - 1 - 1) for the first 48 hours after study inclusion. Patients with evidence for an acute coronary syndrome (Cave: “coronary steal”) or with severe renal dysfunction (Cave: accumulation) will not receive hydralazine, but nitrates only.

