### Important Treatment Rules

- ACE-inhibitor can be administered once or twice per day. ARB should be administered only once a day.
- If Patient is already on ACE-inhibitor or ARB continue dosage unchanged during day 1 and perform up-titration following day 2 till 7 schedule.
- If the patient is already treated with another ACE-inhibitor / ARB than listed in the schedule, previously prescribed ACE-inhibitor / ARB should be continued unchanged during day 1. A daily up-titration of approximate 50% (25% to 75% depending on blood pressure response) starting from day 2 is recommended. The maximal dosage should be achieved at day 5 to 7 of treatment if well tolerated.
- If creatinine levels rise more than 50% from baseline continue ACE-inhibitor / ARB in unchanged dosage to creatinine levels begin to decline. Then continue up-titration according to the treatment schedule.
- If creatinine levels rise more than 100% from baseline reduce ACE-inhibitor / ARB treatment by 50% and continue therapy with unchanged dosage until creatinine levels decline more than 30%.
- Treatment with any diuretics or aldosterone-antagonists at any time is at discretion of treating physician and not determined by the study protocol.

**Figure 5a:** Treatment algorithm for the early goal-directed therapy group (continuation).

On day 3 a further up-titration of the ACE-inhibitor / ARB depends on systolic blood pressure according to Figure 5a will be performed. In patients on LCZ696, the dose of LCZ696 remains unchanged. The dosage of transdermal nitrates will be gradually decreased from day 3 till hospital discharge (Figure 5a). Also, intermittent dosing (12 hours nitrates, 12 hours nitrate-free period) will be used from day 3 on. Typically, we would use in half the dose applied at day 2 and apply the patches from 8:00 h am till 8:00 h pm.

On day 4 till day 7 a further up-titration of the ACE-inhibitor / ARB dependent on systolic blood pressure according to Figure 5a will be performed. In patients on LCZ696 the dose of LCZ696 will be up-titrated by again 25% if not already on target dose (200 mg twice daily).

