### Duration of Treatment with Study-Specific Medication

The study-specific medication with hydralazine in the goal-directed therapy group ends after 48 h after enrolment in the study. The dosage of glycerol trinitrate and up-titration with ACE-Inhibitors and / or ARBs in both groups will be performed according to the treatment algorithms in Figures 5a and 5b during the hospital stay until discharge. Information about discharge medication will be given for both groups; if necessary the discharge summary will provide instructions for maintenance dosage or further up-titration of ACE-inhibitors and / or ARBs to the treating physician in ambulant setting.

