### **p. Safety population**

For the analysis of safety, including protocol pre-defined adverse events, all randomized patients will be included in the safety population if they received at least one dose of the randomized study drug, and had at least one subsequent safety-related visit.

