22 Six days after admission or until discharge from the index hospitalization.

23 **iii. Dose of exposure and concentration**

- 24 – sublingual nitrates: 0.8 mg glyceryl trinitrate, sublingual, 3 times every ten minutes.
- 25 Sublingual nitrates have an approximate onset of action of 1-3 minutes and a half-life
- 26 of 1–4 min.
- 27 – hydralazine 25 mg p.o. four times a day (QID) for 2 days. Half-life, 2–8 hours,
- 28 – nitroglycerin patches in a dosage between 40 to 80 mg in 24 h depending on systolic
- 29 blood pressure and for 5 days. Elimination half-life takes around 10 minutes.
- 30

31

32

33 **9. Evaluation of patients at follow-up**

34 Patient are contacted at 90, 180 and 360 days follow-up (telephone calls, letters). During the  
35 FU patients will be asked about current medication, functional NYHA class and additionally,  
36 to complete Quality of life (EQ-5D-3L) and Kansas City Cardiomyopathy Questionnaire  
37 (KCCQ).

38 **aa. Follow-up at 90 days**

39 The follow-up 90 days months contains a self-reported medicament list update, potential  
40 endpoints assessment, a functional NYHA class assessment and Quality of Life (EQ-5D-3L)  
41 assessment.

42 **bb. Follow-up at 180 days**

43 The follow-up 180 days months contains a self-reported medicament list update, potential  
44 endpoints assessment, a functional NYHA class assessment and Quality of Life (EQ-5D-3L)  
45 and KCCQ assessment.

46 **cc. Follow-up at 360 days**

47 The follow-up 360 days months contains a self-reported medicament list update, a functional  
48 NYHA class assessment and Quality of Life (EQ-5D-3L) and KCCQ assessment.

49 .

50

51 **10. Evaluation of efficacy parameters**

52 **dd. Analysis of primary, secondary, and other efficacy endpoints**

53 **i. Analysis of primary endpoint**

54 The primary endpoint will be analyzed using survival analysis for cumulative incidence (e.g.  
55 Cox regression, Kaplan-Meier and Hazard Ratio) and log rank testing for significance at 180  
56 days.

57 **ii. Analysis of secondary endpoints**

58 Secondary endpoints will be analyzed using the same approach as for the Primary endpoints  
59 and interaction test (p-value) will be conducted between the treatment group and the sub-  
60 group variables.

61 **iii. Analysis of other endpoints**

62 All other endpoints, including novel biomarkers or neurohormones not yet specified in the  
63 protocol will be analyzed using the same approach as for the **Secondary endpoints**.

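### SAP 11.1.3 ends safety-population event counting at the last nitrate or hydralazine intake, before ACE-inhibitor/ARB up-titration is complete, and admits only nitrate-treated controls; analyses without this cut-off exist, so the point is minor

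*Combined protocol and SAP*

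**What the plan says.** SAP 5.6 names the population for safety: "For the analysis of safety, including protocol pre-defined adverse events, all randomized patients will be included in the safety population", on condition that they had a dose of study drug and a later safety visit. It sets no time limit on events.

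SAP 11.1.3 has two parts. The first plans an intention-to-treat comparison of adverse events by chi-square test, with no cut-off at last intake. The second describes the safety population as the "patients who received at least once the study drugs (hydralazine and/or nitrates in the form of capsules, spray and/or transdermal application", and adds "and events are reported up to last confirmed intake of the study drug". ACE inhibitors and ARBs are not among the study drugs in this definition.

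The protocol's description of the early goal-directed group treats them as part of the intervention. The blood pressure target is pursued by "predominately applying nitrates, ACE-inhibitors and ARBs at maximal tolerable" doses. SAP 8.2.1 lists their up-titration under extent of exposure. On timing, the protocol's Important Treatment Rules say of ACE inhibitors and ARBs not listed in the schedule: "The maximal dosage should be achieved at day 5 to 7 of treatment if well tolerated". SAP 8.2.2 gives the duration of exposure as: "Six days after admission or until discharge from the index hospitalization". SAP 8.2.3 says that the patch dose depends on "blood pressure and for 5 days".

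**The concern.** The trial's stated aim covers safety as well as efficacy, and protocol section 6 names arterial hypotension as the main expected harm. A safety count should then cover the whole period in which the strategy lowers blood pressure. The SAP 11.1.3 window is tied to two of its components and can close while a third is still being increased. The protocol expects hypotension in that later period: its hypotension rule from day 3 to discharge cuts back the ACE inhibitor or ARB as well as the patches. Creatinine rise and hyperkalemia, also on the SAP's adverse-event list, are cut off in the same way although both are relevant to ACE-inhibitor/ARB dosing.

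The second problem is comparability. In the control arm transdermal nitrates are optional. A control without a nitrate (and without hydralazine, whose higher-dose use is discouraged there) is not in this population and has no last-intake date. Figure 5b sets no stop day for control patches. The comparison would set nearly the whole intervention arm against a subset of controls chosen by treatment after randomization, over a different window.

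**Working it through.** The plan states no figure to reproduce here. The check compares the scheduled end of the study drugs with the schedule of ACE-inhibitor/ARB increases.

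**Step 1. When the window closes, by schedule.**
- Hydralazine: 48 h (protocol, Duration of Treatment with Study-Specific Medication).
- Patches, Figure 5a: on day 4 all four blood pressure columns have a dose. On day 5 only the columns above 130 mm Hg do. On days 6 and 7 the nitrate row is empty.
- SAP 8.2.3: patches for 5 days.

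The last scheduled intake is therefore day 4 (systolic 90-130 mm Hg) or day 5 (above 130).

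**Step 2. Up-titration days outside the window.** Up-titration runs from day 2 to day 7, which is 6 days.
- Last patch on day 4: days 5, 6 and 7 are outside, 3 of 6.
- Last patch on day 5: days 6 and 7 are outside, 2 of 6.

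Events on days 2 to 4 or 5 of the up-titration are still counted.

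**Step 3. Dose change after the window closes.** Figure 5a, systolic 90-110 mm Hg, mg/d. The lowest ratio is the lowest day-7 dose over the highest day-4 dose; the highest ratio is the reverse.

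| Drug | Day 4 | Day 7 | Lowest ratio | Highest ratio |
|---|---|---|---|---|
| Ramipril | 3.75-5 | 10 | 10/5 = 2.0 | 10/3.75 = 2.7 |
| Lisinopril | 5-10 | 20-30 | 20/10 = 2.0 | 30/5 = 6.0 |
| Enalapril | 10-15 | 30-40 | 30/15 = 2.0 | 40/10 = 4.0 |
| Captopril | 50-75 | 150 | 150/75 = 2.0 | 150/50 = 3.0 |
| Candesartan | 12-24 | 24-32 | 24/24 = 1.0 | 32/12 = 2.7 |
| Losartan | 50-75 | 75-100 | 75/75 = 1.0 | 100/50 = 2.0 |

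By schedule every listed ACE inhibitor at least doubles after the last patch day. An ARB may not rise at all.

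**Step 4. How many events this could remove.** The documents give neither length of stay nor hypotension risk by day, so only an illustration on assumed inputs is possible. Let S be the stay in days, w the last patch day, and k the daily risk after w relative to the risk before. The share outside the window is k(S - w) / (w + k(S - w)).
- S = 7, w = 4: k = 0.25 gives 0.75/4.75 = 16%; k = 1 gives 3/7 = 43%; k = 2 gives 6/10 = 60%.
- S = 7, w = 5: k = 0.25 gives 0.5/5.5 = 9%; k = 1 gives 2/7 = 29%; k = 2 gives 4/9 = 44%.
- S = 4, w = 4: 0%.

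A range of 0% to 60% means that the documents do not determine the loss.

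**Step 5. Direction.** In the intervention arm the cut-off can only remove events. In the control arm it also acts through who enters, so the net effect on the difference between arms has no derivable sign.

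**The case against.** The strongest reply is that the SAP already holds analyses without this cut-off. The only adverse-event comparison with a stated test is the intention-to-treat one in SAP 11.1.3. Supplemental Table 1 is titled for all patients, shows patients with each event by arm, and has rows for hypotension, creatinine and potassium. Symptomatic hypotension over the initial hospitalization is a secondary endpoint, analysed by intention to treat and shown in Table 3 of the main publication. An on-treatment count beside an intention-to-treat count is a common pairing. All of this stands. A reader might infer that late hypotension goes unreported; the documents do not support that.

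The closing day is also less settled than Figure 5a suggests. The protocol text after that figure describes a nitrate taper from day 3 until the patient leaves hospital. The duration section says that nitrate dosing, as well as ACE-inhibitor/ARB up-titration, "will be performed according to the treatment algorithms in Figures 5a and 5b during the hospital stay until discharge". The SAP rule uses each patient's last confirmed intake, not the scheduled day, so some windows will run longer than day 5.

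What remains is narrower. SAP 5.6 assigns the analysis of safety to the restricted population, and nothing says which count supports a statement that the strategy is safe. Supplemental Table 1 is planned only where applicable and on request. No uncut analysis repairs the selection of controls within the safety population itself.

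**Conclusion.** The point holds for the safety population and is minor. On the Figure 5a schedule, for a patient still in hospital, the last 3 or 2 of 6 up-titration days fall outside its event window. The control side is a subset selected after randomization with a window of its own. This rests on reading the study drugs as SAP 11.1.3 defines them and the last patch as day 4 or 5. A stay of 4 days or less loses nothing, and a patient whose patches continue to discharge loses little or nothing.

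Two stronger readings are tempting and should not be drawn. One is a stated percentage of missed events: every such figure needs an assumed stay and an assumed daily risk. The other is that the plan makes the intervention look safer than control: the intervention-arm count is truncated, but the control subset may carry a higher or lower risk than all controls, so the net bias is unknown.

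**What to change.** In SAP 5.6 and 11.1.3:

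1. Make the lead safety analysis the number (%) of patients with at least one event from randomization to discharge from the index hospitalization, in all randomized patients in both arms. State that Supplemental Table 1 is always produced on this basis.
2. If an on-treatment analysis is kept, define study treatment as the whole strategy: nitrates, hydralazine and in-hospital ACE-inhibitor/ARB up-titration. Use one window for both arms, day 7 or discharge, whichever comes first, and include all controls.

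The cost is a text change. SAP 11.1 already has the listed adverse events documented over the index hospitalization, so no new data are needed. The downside is that a full-stay count includes events less attributable to nitrates, and the intervention-arm rate will be at least as high as the truncated one.
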